10.3.4.1. Visit 4 or Early Withdrawal (Study Exit)

The following procedures and assessments will be conducted in association with Visit 4:

- vital signs ([Section 10.2.4](#));
- height of subject ([Section 10.2.5](#));
- total body weight of subject ([Section 10.2.5](#));
- targeted physical examination ([Section 10.2.6](#));
- serum chemistry panel, only if Visit 4 represents an Early Withdrawal Visit ([Section 10.2.11.2](#));
- serum bicarbonate and serum potassium; not needed if Visit 4 represents an Early Withdrawal Visit ([Section 10.2.11.6](#));
- review of ADV7103 dosing diary ([Section 10.2.12](#));
- concomitant medications ([Section 10.2.13](#));
- adverse events ([Section 10.2.14](#));
- completion of questionnaires ([Section 10.2.13](#)), only if the visit represents an Early Study Withdrawal Visit after at least 4 weeks of study participation;
- arrangement for semi-structured interview ([Section 10.2.16](#)), only if the visit represents an Early Study Withdrawal Visit after at least 4 weeks of study participation;
- collection of empty boxes of ADV7103 and unused ADV7103 for this study; and
- ADV7103 accountability ([Section 10.2.20](#)).

10.3.5. Unscheduled Visits

The Investigator or her/his designee may schedule a visit to the subject's home via telehealth or if feasible ask the subject to visit the investigational site for a variety of reasons depending on the clinical status of the subject. Laboratory and other tests are not mandatory for Unscheduled

Visits but may be performed at the Investigator's discretion. The following procedures and assessments can be conducted in association with Unscheduled Visits:

- vital signs ([Section 10.2.4](#));
- targeted physical examination ([Section 10.2.6](#));
- serum chemistry panel ([Section 10.2.11.2](#)), if the visit represents a study withdrawal visit;
- 12-lead ECG ([Section 10.2.8](#)), if clinically indicated for serum potassium < 3.0 mEq/L;
- concomitant medications ([Section 10.2.13](#)); and
- adverse events ([Section 10.2.14](#)).

11. ASSESSMENT OF SAFETY

11.1. Safety Parameters

The safety of ADV7103 will be assessed, in part, using parameters included in Section 10.2.1 through Section 10.2.11.7. Adverse events (AEs), defined in Section 11.2.1, will be captured during every study encounter following signature of the informed consent form.

11.2. Adverse Events and Serious Adverse Events

11.2.1. Definitions

11.2.1.1. Adverse Event (AE)

An AE is defined as any untoward medical occurrence in a subject administered an IP or has undergone study procedures and which does not necessarily have a causal relationship with this treatment. An AE can therefore be any unintended sign (including an abnormal laboratory finding), symptom, or disease temporally associated with the use of the IP, whether or not related to the IP.

An abnormality identified during a medical test (eg, laboratory parameter, vital sign, ECG data, physical examination finding) should be defined as an AE only if the abnormality meets at least one of the following criteria:

- induces clinical signs or symptoms;
- requires active intervention;
- requires interruption or discontinuation of the IP;
- the abnormality or test result is clinically significant in the opinion of the Investigator.

11.2.1.2. Serious Adverse Event (SAE)

An AE is considered “serious” if, in the view of either the Investigator or Sponsor, it:

- results in death;
- is life threatening (An AE is considered “life-threatening” if, in the view of either the Investigator or Sponsor, its occurrence places the subject at immediate risk of death. It does not include an adverse event that, had it occurred in a more severe form, might have caused death);
- results in persistent or significant disability/incapacity or substantial disruption of the ability to conduct normal life functions;
- results in a congenital anomaly or birth defect;
- requires inpatient hospitalization or leads to prolongation of hospitalization (hospitalization for treatment/observation/examination caused by AE is to be considered as serious); or
- represents a medically important event as determined by the Investigator.

Medical and scientific judgment should be exercised in deciding whether AEs are serious, such as important medical events that may not be immediately life-threatening or result in death or hospitalization but may jeopardize the subject and may require medical or surgical intervention to prevent one of the other outcomes listed in the definition above. These events, including those that may result in disability/incapacity, should also usually be considered serious. Examples of such events are intensive treatment in an emergency room or at home for allergic bronchospasm; blood dyscrasias or convulsions that do not result in hospitalization; or development of drug dependency or drug abuse.

The following are not considered SAEs:

- hospitalization for elective or preplanned treatment for a pre-existing condition unrelated to the condition under study and which has not worsened since informed consent; and
- hospital admission due to social or situational events (eg, travel conditions that interfere with ability to leave hospital setting).

11.2.1.3. Suspected Unexpected Serious Adverse Reaction (SUSAR)

A suspected unexpected serious adverse reaction (SUSAR) is any adverse drug reaction (ADR) that is serious, unexpected, and suspected, meaning there is a reasonable possibility that the IP caused the adverse event. An AE or suspected adverse reaction (ie, an AE related to the IP) is considered "unexpected" if it is not listed in the IB or is not listed at the specificity or severity that has been observed.

11.3. Relationship of Adverse Event to Study Product

An Investigator who is qualified in medicine must make a determination of relationship to the study product for each AE. [Table 3](#) includes the criteria for determining relationship between the AE and the study product.

Table 3: Criteria for Determining Causal Relationship to the Study Product

Causal Relationship to the Study Product	Criteria for Determining Causal Relationship
Definitely Related	There is clear evidence to suggest a causal relationship, and other possible contributing factors can be ruled out. The clinical event, including an abnormal laboratory test result, occurs in a plausible time relationship to administration of the study product and cannot be explained by concurrent disease or other devices, drugs, or chemicals.
Possibly Related	There is some evidence to suggest a causal relationship (eg, the event occurred within a reasonable time after administration of the study product). However, the influence of other factors may have contributed to the event (eg, the subject's clinical condition, other concomitant events). Although an adverse effect may rate only as "possible" soon after discovery, it can be flagged as requiring more information and later be upgraded to probable or certain as appropriate.
Unlikely Related	A clinical event, including an abnormal laboratory test result, whose temporal relationship makes a causal relationship improbable (eg, the event did not occur within a reasonable time after administration of the study product) and in which other drugs or chemicals or underlying disease provide plausible explanations (eg, the subject's clinical condition, other concomitant treatments).
Not Related	A clinical event, including an abnormal laboratory test result, which occurs when the subject was not exposed to the study product or, another cause is obvious and in which there is sufficient information that the etiology of the event is not related to the study product.

If the relationship between the AE and the study product is determined to be "definitely related" or "possibly related," the AE will be considered to be related to the study product for the purposes of expedited regulatory reporting.

11.4. Severity of an Adverse Event

The severity of AEs, including abnormal clinical laboratory results, will be assessed according to the criteria in [Table 4](#).

TBDpTable 4: Criteria for Determining the Severity Grade of an Adverse Event

Severity Grade	Severity Assessment Standard
Grade 1 (Mild)	The AE requires minimal or no treatment. The AE doesn't interfere with the subject's daily activities.
Grade 2 (Moderate)	The AE results in a low level of inconvenience or concerns with the therapeutic measures. The AE may cause some interference with functioning or reduction with the usual level of activity of the subject.
Grade 3 (Severe)	The AE may require systemic drug therapy or other treatment. The AE causes a significant impairment of functioning, interrupts a subject's usual daily activity and is usually incapacitating.

Changes in the severity of an AE should be documented to allow an assessment of the duration of the event at each level of intensity to be performed. Adverse events characterized as intermittent require documentation of the onset and duration of each episode.

It is important to distinguish between SAEs and severe AEs. Severity is a measure of intensity whereas seriousness is defined by the criteria listed in Section 11.2.1.2. An AE of severe intensity may not be considered serious.

11.5. Reporting Adverse Events

11.5.1. All Adverse Events

At each study visit (on-site or via telephone), the subject will be questioned in a general manner, and no specific signs or symptoms will be suggested. If any AEs have occurred, they will be recorded on the AE pages of the electronic case report form (eCRF) and in the subject's medical record. If known, the diagnosis should be recorded in preference to the listing of individual signs and symptoms.

11.5.2. Serious Adverse Events

Any SAE which occurs at any time following informed consent through the last study visit, whether or not causally related to the study product, must be reported by the Investigator to CTI Safety immediately (**no later than 24 hours after learning of its occurrence**):

Vigipharme Global Safety & Pharmacovigilance

SAE eFax #: [name]

E-mail: [contact]

If there are any questions, or if clarification is needed regarding the SAE, please contact the Medical Monitor for this study ([Table 1](#)).

Follow-up information for the event should be sent promptly (within 7 days of the initial notification).

Full details of the SAE should be recorded on the medical records and in the eCRF. The following minimum information is required:

- study number (B23CS);
- subject number, gender and age;
- date of report;
- description of the SAE (event, seriousness of the event); and
- causal relationship to the study product.

Advicenne Pharma or its designee will submit expedited safety reports to the regulatory agencies as necessary, and will inform the investigators of such regulatory reports. Investigators must submit safety reports as required by their IRB/IEC within timelines set by applicable regulations. Documentation of the submission to and receipt by the IRB/IEC of expedited safety reports should be retained by the site.

Investigators will also be notified of all unexpected, serious, study product-related events (7/15 day safety reports) that occur during the clinical study. Each site is responsible for notifying its IRB or IEC of these additional SAEs.

11.6. Duration of Adverse Event Follow Up

If any AEs are present when a subject completes her/his last study visit (including early termination, if applicable), the subject will be re-evaluated within an appropriate period of time. At the Investigator's discretion, minor AEs can be re-evaluated via telephone and documented. If the AE has still not resolved, additional follow up will be performed as appropriate. Every effort should be made by the Investigator or her/his delegate to contact the subject until the AE has resolved or stabilized or the Medical Monitor and Investigator agree that further follow up is not necessary. This should be documented in the subject's medical records.

11.7. Reporting of Pregnancy

If a subject becomes pregnant during study participation, basic information about the pregnancy will be recorded in the Pregnancy eCRF and submitted to CTI Safety. Pregnancy in itself is not regarded as an AE unless there is a suspicion that a study product may have interfered with the effectiveness of a contraceptive medication. If there are complications during the pregnancy, the complications are recorded as AEs. The subject will be asked to report the outcome of the pregnancy even if her study participation is discontinued, and the site should submit the information to CTI Safety within 30 days after the outcome of the pregnancy. All reports of congenital abnormalities/birth defects are SAEs to be entered on the mother's (ie, subject's) SAE form. Spontaneous miscarriages should also be reported and handled as SAEs. Elective abortions without complications should not be reported as AEs. Partner pregnancies do not need to be reported.

11.8. Data Monitoring Committees

11.8.1. Unblinded Data Monitoring Committee

An uDMC will be established to review study data and approve randomization of subjects following blinded dosing of study product in the initial age group. Starting with the oldest group (≥ 12 years old), each subsequently younger group will be randomized after 4 subjects from the preceding older age group have completed Period 3 and the uDMC approves randomization in the next younger group. During uDMC review of data from an age group, enrollment into that age group may continue unless the uDMC recommends cessation of this activity. The uDMC may request additional subjects complete the study in the age group under uDMC review prior to approving randomization of the next younger group. In addition, after reviewing data from randomized subjects who do not complete the Withdrawal Period, the uDMC may recommend changes to the protocol (including, but not limited to, increasing the total number of subjects enrolled in the study) to ensure a reasonable balance of early withdrawals between treatment groups. Lastly, if laboratory data, clinical symptoms, and cardiac monitoring data warrant, the uDMC may recommend modification of cardiac monitoring.

The uDMC will consist of individuals who are not directly involved in the conduct of the study. All uDMC activities will be organized to ensure that blinding is preserved for Investigators, the Sponsor, and Sponsor representatives during study conduct. A charter will be prepared to further describe membership and the roles and responsibilities of the uDMC.

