7.3. Subject Withdrawal Criteria

Subjects will be withdrawn from the study if any of the following apply:

- failure to achieve targeted serum bicarbonate levels as specified in this protocol;
- failure to achieve targeted serum potassium levels as specified in this protocol;
- occurrence of an adverse event related to the study product, placing the subject at an unacceptable risk with continued study participation (as determined by the Investigator);
- pregnancy;
- significant nonadherence to treatment or study procedures as determined by the Investigator; or
- withdrawal of informed consent.

All subjects withdrawn from the study should complete assessments associated with Visit 4 in [Section 17.1](#). There is no plan to replace randomized subjects who are withdrawn from the study. If a subject is withdrawn from the study due to an adverse event, the subject will be followed as specified in [Section 11.6](#).

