8.4. Randomization and Blinding

Randomization will be completed and prior to blinded study product administration. It is expected that subjects will consent (or assent, when applicable) to participation in Periods 1 through 4 during the Screening Visit.

After admission into Period 3, and completion of baseline evaluations, subjects will either continue their stabilized ADV7103 dose or switch to a weight-matched identical-appearing placebo dose according to their randomized treatment assignment (without potassium supplementation).

The Investigator and staff (except for the pharmacist) will be blinded to Period 3 study product assignments but will have access to laboratory results and other information pertinent to clinical care of the subjects. The pharmacist will be unblinded to treatment assignment for the purposes of preparing, controlling, dispensing study product and documenting accountability of study product.

Unblinded DMC members will have access to Period 3 treatment assignments in order to interpret Period 3 data and make recommendations concerning sequential randomization of age groups or any potential safety issues ([Section 11.8.1](#)).

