12. STATISTICS

12.1. Number of Subjects

Approximately 40 subjects will enter the Open-label Lead-in Period (Period 2), so that at least 32 are randomized and complete the Withdrawal Period (Period 3). Sixteen evaluable subjects per arm provides at least 90% power to show superiority of ADV7103 over placebo in the proportion of subjects who develop hyperchloremic metabolic acidosis up to Day 6. This calculation assumes that approximately 85% of placebo subjects and 15% of ADV7103 subjects will develop hyperchloremic metabolic acidosis. Significance will be assessed at the 2-sided 5% level.

Randomization will be stratified according to the following age categories:

- 6 months - 23 months old
- 2 - 11 years old
- ≥ 12 years old.

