12.8. Interim Analysis

No formal interim analysis of efficacy is planned.

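### The unblinded committee may recommend a larger sample to balance withdrawals between arms, which more enrolment does not achieve, and nothing in the plan keeps that recommendation independent of outcome by arm

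*Combined protocol and SAP*

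**What the plan says.** **The power.** Under 11.8.1, once the uDMC has reviewed randomized subjects who did not complete the Withdrawal Period, it may recommend protocol changes, among them "increasing the total number of subjects enrolled in the study) to ensure a reasonable balance of early withdrawals between treatment groups". The Synopsis (Study Design and Methodology), 4.2.2 and 6.1 repeat this.

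**What the committee sees.** Section 8.4: "Unblinded DMC members will have access to Period 3 treatment assignments in order to interpret Period 3 data". The purposes given there are release of the younger age groups and safety. The reviews described in 11.8.1 start after 4 completers in an age group. No timing is given for the review of non-completers.

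**Who decides.** Under 6.7 the sponsor considers the recommendation. Under 11.8.1 the sponsor stays blinded. Under 13.6 a substantial amendment needs regulatory and ethics approval.

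**The analysis.** Section 12.1: "Approximately 40 subjects will enter the Open-label Lead-in Period (Period 2), so that at least 32 are randomized and complete the Withdrawal Period". Also 12.1: "Significance will be assessed at the 2-sided 5% level". Section 12.3 uses a CMH test stratified by age, on the ITT set. Section 12.5 controls type I error across endpoints only. Section 12.8: "No formal interim analysis of efficacy is planned". No section gives a trigger, cap, decision rule or adjusted test for a change in N. A uDMC charter is promised but is not among the documents.

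**The concern.** There are two problems.

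1. **The tool does not fit the purpose.** Early withdrawal happens after randomization and may be caused by treatment. Enrolling more subjects does not change the expected difference between arms in the rate of withdrawal. It only narrows the random variation around that difference.

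2. **The primary test has no stated protection.** The people who may propose a larger N also hold the primary outcome by arm. If the proposal depends on that outcome, even informally, the ordinary 5% test no longer has exactly 5% error. In a confirmatory trial of about 32 randomized subjects, an increase proposed by an unblinded committee, with no written rule, invites the question whether N was raised because the result was not yet significant.

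**Working it through.** **Inputs from 12.1.** 16 evaluable subjects per arm; event rates 85% (placebo) and 15% (ADV7103); two-sided 5%. Equal allocation is inferred from 16 per arm. Look times, size of increase and withdrawal rates are not in the documents, so those below are assumptions.

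**1. The plan's own power figure.** Section 12.1: "Sixteen evaluable subjects per arm provides at least 90% power to show superiority of ADV7103 over placebo". Normal approximation, pooled variance under the null:

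(0.70 × √16 − 1.96 × √(2 × 0.5 × 0.5)) / √(2 × 0.85 × 0.15) = (2.80 − 1.386) / 0.505 = 2.80, so power = 99.7%.

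Exact enumeration gives 99.5% (Mantel-Haenszel) and 98.4% (Fisher). The stated floor is correct. For 90% power, n = (1.386 + 1.282 × 0.505)² / 0.70² = 8.4, so 9 per arm (12 with continuity correction). Under the plan's assumptions N = 32 has room to lose subjects.

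**2. Does more enrolment balance withdrawals?** With n per arm and withdrawal rates w₁ and w₂, the expected rate gap is w₁ − w₂ and the expected count gap is n(w₁ − w₂).

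| Assumed rates | n per arm | Expected rate gap | Expected count gap | SD of rate gap |
|---|---|---|---|---|
| 25% vs 5% | 16 | 20 points | 3.2 | 0.121 |
| 25% vs 5% | 24 | 20 points | 4.8 | 0.099 |
| 25% vs 5% | 32 | 20 points | 6.4 | 0.086 |
| 10% vs 10% | 16 | 0 | 0 | √(2 × 0.1 × 0.9 / 16) = 0.106 |
| 10% vs 10% | 32 | 0 | 0 | √(2 × 0.1 × 0.9 / 32) = 0.075 |

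A systematic gap keeps its rate and grows in count. Only chance imbalance shrinks.

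**3. Type I error if N depends only on withdrawals unrelated to outcome.** The error is then a weighted average of the sizes of the fixed designs. For the exact unstratified Mantel-Haenszel test at a 50% null rate these are 5.0% (16 per arm) and 5.95% (24 per arm); at a 15% null rate, 4.2% and 5.4%. The result is near 5%, and the departures come from discreteness, not from adapting N.

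**4. Type I error if N follows outcome by arm, specific rules.** Simulation, 50% null rate, final test unadjusted. Add 8 per arm when 1.0 ≤ |z| < 1.96 at the look:

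| Look, per arm | Type I error |
|---|---|
| 4 | 5.2% |
| 8 | 5.2-5.3% |
| 12 | 5.7% |
| 16 (all 32 outcomes) | 8.1% |

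At a 30% null rate, looks at 4 to 12 per arm give 4.5-4.9%. After all 32 outcomes (50% null rate), adding 4 per arm under the same rule gives 6.6%, and adding 16 per arm after any non-significant result gives about 9.1%.

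**5. Worst case, normal theory.** With n₁ subjects seen and interim z₁, the chance of rejecting at final size N is

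CP(z₁, N) = Φ((z₁√n₁ − 1.96√N) / √(N − n₁)) + Φ((−z₁√n₁ − 1.96√N) / √(N − n₁)).

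Take the N that maximizes this for each z₁ and average over the null distribution of z₁:

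| Subjects seen | N up to 40 | N up to 48 | N up to 64 |
|---|---|---|---|
| 8 | 5.25% | 5.43% | 5.65% |
| 16 | 5.47% | 5.79% | 6.20% |
| 24 | 5.75% | 6.22% | 6.81% |
| 32 | 7.09% | 7.80% | 8.63% |

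Exact enumeration with N up to 64 (null rates 15% to 85%) gives 6.0-6.9% after 16 subjects, 6.6-7.6% after 24 and 8.2-9.4% after 32. Fixed designs give 4.2-5.0% at N = 32 and 5.2-6.0% at N = 64, so part of the excess is discreteness.

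**6. With protection.** A combination test with weights fixed in advance from N = 32 gives 5.00% in normal theory for looks at 8, 16 or 24 subjects, whatever N is then chosen.

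**The case against.** **What stands.** The uDMC recommends; a blinded sponsor decides, and an amendment needs outside approval. The stated trigger is withdrawals, and no section gives the committee an efficacy test, so 12.8 is not contradicted. The reviews described come early, where the inflation is small. The charter may hold a trigger or cap. Chance imbalance does shrink with N, and at this size much of an observed imbalance could be chance. A pooled count cannot show differential dropout.

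**What does not answer the point.** A recommendation formed from unblinded data carries that information to the sponsor's decision, however blinded the sponsor is. The trigger does not separate withdrawals from outcome, because the committee holds both and has no written rule. The protocol text creates the power and is where its limit belongs.

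**Stronger readings that the documents do not support.**

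- A reader might infer that the imbalance to be corrected is the treatment effect itself, since 12.1 assumes that "approximately 85% of placebo subjects and 15% of ADV7103 subjects will develop hyperchloremic metabolic acidosis" and an event stops blinded product. But 6.2.3 and 10.2.18 keep these subjects under monitoring in Period 3 for about 6 days or until corrected. Stopping product is not leaving the period.
- A reader might see a conflict with 7.3: "There is no plan to replace randomized subjects who are withdrawn from the study". Not replacing individuals is compatible with a later amendment that enlarges the trial.
- A reader might conclude that the plan has an 8-9% error rate. That needs an extension driven by the primary result after all 32 outcomes, and no such review is described.

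**Conclusion.** The point holds as a weakness in the wording of the uDMC's remit. It does not show that the primary test is already inflated. The stated purpose cannot be met by enrolment when withdrawal is related to treatment, and the plan does not keep an N recommendation independent of outcome by arm.

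The size depends on facts that the documents do not give. Error stays near 5% if only withdrawal counts unrelated to outcome are used. It is about 5.2-5.7% for 8 more per arm after a promising z at 4 to 12 per arm. Normal-theory worst cases are roughly 5.3-7% before all 32 outcomes are in (up to 7.6% by exact enumeration after 24 subjects). It is about 7-9% if N is extended after all 32. With power near 99% under the plan's own assumptions, the unblinded route to a larger N buys little, so closing it is a cheap improvement.

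**What to change.** 1. **Narrow the remit.** In the Synopsis, 4.2.2, 6.1 and 11.8.1, delete the words "increasing the total number of subjects enrolled in the study) to ensure a reasonable balance of early withdrawals between treatment groups" together with the opening of the parenthesis in front of them. Deleting only the balance clause would leave the uDMC a power over N with no stated purpose. Because 6.7 separately lets the uDMC recommend protocol modifications for safety or other reasons, add that these exclude sample size.

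2. **Add a blinded rule in 12.1.** N may be raised, up to a stated cap, only when the pooled, blinded count of randomized subjects with an evaluable primary outcome is projected to fall below 32. State that an acidosis event counts as evaluable and as completing. The sponsor or the blinded committee decides, without arm data.

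3. **If the uDMC is to keep the power,** pre-specify in 12.3 a fixed-weight combination (conditional-error) test, with weights taken from N = 32 and the decision made before all 32 outcomes are known.

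4. **Handle differential withdrawal in the analysis,** through the multiple-imputation and worst-case ITT analyses already planned in 12.6.

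**Cost.** A protocol amendment with its approvals, and matching charter text. The uDMC loses the ability to propose a larger N from withdrawals by arm. Its safety and age-group release roles are unchanged.
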